### **4.1. Screened Set**

The screened set consists of all subjects who provided written informed consent and are screened for participation in this study. This population will only be used for the purposes of describing the subject disposition and for listing the data.

### **4.2. Intent-to-Treat Set**

The Intent-to-treat (ITT) set consists of all randomized subjects. Subjects will be analyzed in the treatment arm assigned at randomization.

### **4.3. Modified Intent-to-Treat Set**

The modified ITT (mITT) set consists of all randomized subjects who receive at least one injection of pegcetacoplan or sham and have baseline and at least one post-baseline value of GA lesion area in the study eye as assessed by FAF. Subjects will be analyzed in the treatment arm assigned at randomization.

### **4.4. Safety Set**

The Safety set consists of all subjects randomized who receive at least one injection of pegcetacoplan or sham. Subjects will be analyzed according to the actual treatment received. In the case a subject received an incorrect injection of study medication than what they were randomized to, subjects will be presented under the corresponding pegcetacoplan arm if they received at least one injection of pegcetacoplan during the study and will only be presented under the corresponding sham arm if they did not receive any injections of pegcetacoplan. This population will be used for all safety analyses.

### **4.5. Per-Protocol Sets**

The Per-Protocol (PP) sets will be identified separately for Month 12 and Month 24 analysis, respectively (i.e., Month 12 PP set and Month 24 PP set). The PP sets consist of all mITT subjects who have a valid GA lesion area assessment for either Month 10 or 12 (Month 12 PP set) or a valid GA lesion area assessment for at least one of Month 18, 20, 22, 24 (Month 24 PP set) and who follow the protocol without any major deviation(s) that could affect the primary efficacy data.

A valid GA lesion area assessment is defined as a non-missing measured GA lesion area assessment at a given timepoint where at least 75% of the expected injections over the course of participation ahead of the given timepoint have been received by the subject. For example:

- A valid GA lesion measurement at Month 10 in the Monthly arm would be a result available at Month 10 with no more than 2 missed injections prior to the Month 10 assessment (10 scheduled before Month 10, 2 missed = 80% compliance).

- A valid GA lesion measurement at Month 20 in the every other month (EOM) arm would be a result available at Month 20 with no more than 2 missing injections prior to the Month 20 assessment (10 scheduled before Month 20, 2 missed = 80% compliance).

Major protocol deviations (PDVs) that lead to exclusion from the Month 12 PP set and the Month 24 PP set are as follows:

(i) Violations of inclusion and/or exclusion criteria

A PDV with any of the following inclusion and/or exclusion criteria violations will be classified as a major PDV:

Inclusion Criterion #3: Clinical diagnosis of GA of the macula secondary to AMD as determined by the Investigator and confirmed by the Reading Center

Inclusion Criterion #4: The GA lesion must meet the criteria listed in the protocol as determined by the central Reading Center's assessment of FAF

- Total GA area must be  $\geq 2.5$  and  $\leq 17.5$  mm^2 (1 and 7 disk areas [DA] respectively).
- If GA is multifocal, at least one focal lesion must be  $\geq 1.25$  mm^2 (0.5 DA), with the overall aggregate area of GA as specified above in 4a.
- The entire GA lesion must be completely visualized on the macula centered image and must be able to be imaged in its entirety and not contiguous with any areas of peripapillary atrophy.
- Presence of any pattern of hyperautofluorescence in the junctional zone of GA. Absence of hyperautofluorescence (i.e., pattern = none) is exclusionary.

Exclusion Criterion #1: GA secondary to a condition other than AMD such as Stargardt disease, cone rod dystrophy or toxic maculopathies like plaquenil maculopathy in either eye.

Exclusion Criterion #3: Any history or active choroidal neovascularization (CNV), associated with AMD or any other cause, including any evidence of retinal pigment epithelium rips or evidence of neovascularization anywhere based on spectral domain optical coherence tomography (SD-OCT) imaging and/or fluorescein angiography as assessed by the Reading Center.

Exclusion Criterion #13: Prior participation in another interventional clinical study for geographic atrophy in either eye including investigational oral medication and placebo.

(ii) Not receiving assigned treatment

Not receiving assigned treatment at more than 25% of the treatment visits over the analysis timeframe, either 12-month or 24-month, will be classified as a major PDV.

## 4.6. Genotyping Set

The genotyping set consists of all ITT subjects who have at least one non-missing genotyping result for a single nucleotide polymorphism (SNP) associated with age-related macular degeneration from the genotype sequencing analysis.

## 5. STUDY SUBJECTS

### 5.1. Disposition of Subjects

The number of subjects screened, passed screening, screened failed, and the reasons for screen failure will be presented overall.

The number of subjects randomized and in each defined analysis set will be summarized by treatment group and overall for the ITT Set. In addition, the reasons for exclusion from the mITT and per-protocol populations will be summarized.

Subjects' disposition by region and country will also be provided for the ITT set. All summaries on subject disposition will be produced based on the Month 12 dataset for the Month 12 reporting and based on the final study dataset for the final reporting, as appropriate.

Overall summary of subjects' disposition includes:

- Number of subjects randomized
- Number of subjects completed treatment [through Month 12 or Month 24, as appropriate]
- Number of subjects discontinued from treatment and reason for discontinuation [prior to Month 12 or Month 24 as appropriate]
  - Subjects who discontinued from treatment without concurrent study discontinuation will be singled out [prior to Month 12 or Month 24 as appropriate]
- Number of subjects completed study [through Month 12 or Month 24, as appropriate]
- Number of subjects discontinued from study and reason for discontinuation [prior to Month 12 or Month 24 as appropriate]

A summary of the disposition through each study visit will also be presented by treatment group and overall for the ITT set.

In addition, to assess the impact of COVID-19 pandemic on disposition of subjects, the following summary will be provided for each study visit and by reason (COVID-19 vs. non-COVID-19) for the ITT set:

- Number of subjects discontinued from treatment
- Number of subjects discontinued from study

## 5.2. Demographic and Other Baseline Characteristics

Demographic and baseline characteristics will be tabulated using descriptive statistics by treatment group and overall. Tables will be produced for the following analysis sets: ITT, Safety, mITT, Month 12 PP and Month 24 PP (as appropriate), and Genotyping. The following variables will be included in the tables:

The demographic data are:

- Age at screening (years) and in categories
  - < 65
  - 65-<75
  - 75-<85
  - $\geq 85$
- Sex
- Race
- Ethnicity
- Geographic Region (United States vs. Rest of World)
- Country
- Weight (kg) at baseline
- Height (cm) at baseline
- Body Mass Index ( $\text{kg}/\text{m}^2$ )
- Tobacco use status (ever, never)

Baseline characteristics will be summarized for both study eye and fellow eye whenever applicable. Baseline characteristics include:

- Study eye laterality (OD, OS)
- Study eye status (better-seeing eye vs. worse-seeing eye, based on NL-BCVA – in the case of ties, study eye status will be classified as the better-seeing eye)
- GA lesion size ( $\text{mm}^2$ ) (assessed by FAF)
- GA lesion size in categories, determined by reading center (as randomized status and actual status):
  - <  $7.5 \text{ mm}^2$
  - $\geq 7.5 \text{ mm}^2$
- GA lesion size categories (approximately tertiles based on APL2-303/304 combined data\*) – study eye only
- Square root GA lesion size (mm)

- GA lesion location (subfoveal involvement vs. non-subfoveal involvement) (assessed by FAF)
- GA focality (unifocal vs. multifocal) (assessed by FAF)
- Number of areas of atrophy (none, 1, 2-5, 6-10, 11-20, >20, cannot be determined) (assessed from FAF)
- Presence of double-layer sign (DLS) (assessed by SD-OCT)
- Central subfield thickness (CST) (assessed by SD-OCT)
- Presence of macular neovascularization (MNV) (i.e., subclinical CNV) (assessed by Optical Coherence Tomography Angiography (OCT-A))
- Presence of pseudodrusen (assessed by near-infrared reflectance imaging)
- Number of intermediate/large drusen (0-5, 6-10, 11-20, and >20) (assessed by color fundus photography)
- NL-BCVA in ETDRS letters
- NL-BCVA categories ( $\geq 70$ ,  $\geq 60 - < 70$ ,  $\geq 35 - < 60$ ,  $< 35$  ETDRS letters)
- NL-BCVA ( $< 60$  vs.  $\geq 60$  ETDRS letters)
- LL-BCVA in ETDRS letters
- LL-BCVA categories (approximately tertiles based on APL2-303/304 combined data\*) – study eye only
- IOP
- LLD in ETDRS letters
- LLD categories ( $< 20$  vs.  $\geq 20$  ETDRS letters)
- LLD categories (approximately tertiles based on the APL2-303/304 combined data\*) – study eye only
- NL-BCVA ( $< 60$  vs.  $\geq 60$  ETDRS letters) and LLD ( $< 20$  vs.  $\geq 20$  ETDRS letters) combinations
- Advanced AMD (fellow eye with: GA only, GA with CNV, CNV only, neither GA nor CNV)
- GA laterality (bilateral GA vs. study eye GA Only)
- Presence of CNV in fellow eye (as randomized and actual status (based on medical history))
- Lens status:
  - Phakic
  - Pseudophakic
- Reading speed assessment method

- Monocular and binocular maximum reading speed and critical print size (without adjustment for reading inaccuracy)
- Monocular maximum reading speed categories (<60, 60-<160, ≥160 words per minute (wpm))
- Monocular maximum reading speed categories (approximately tertiles based on APL2-303/304 combined data\*) – study eye only
- Mean FRI Index score
- FRI Level (1,2,3,4)
- Mean threshold sensitivity of (assessed by microperimetry)
  - All points
  - Perilesional points
  - Paralesional points
  - Extralesional points
- Mean threshold sensitivity of all points categories (approximately tertiles)
- Number of scotomatous points (assessed by microperimetry)
- Fixation stability (95% BCEA) (assessed by microperimetry)
- Fixation stability (95% BCEA) categories (approximately tertiles)
- NEI VFQ-25 distance activity subscale score
- NEI VFQ-25 near activity subscale score
- NEI VFQ-25 driving subscale score
- Number of subjects currently driving at baseline
- NEI VFQ-25 composite score
- Dry AMD status (iRORA, large drusen) (at Month 24 reporting only)

\*Approximately tertiles will be specified consistently across the APL2-303/304 studies to the nearest clinically relevant level.

Baseline will be defined as the last available pre-treatment value taken on or before the first dose date of study drug. In the case a subject did not receive study drug in the ITT population, the last assessment prior to study exit will be used as baseline.

Conversions for height and BMI are as follows:

- Height (m) = Height (cm) x 0.01
- Body mass index (kg/m^2) = Weight (kg) / [Height (m)]

Demographics and baseline characteristics will also be listed for the ITT set.

### **5.3. Medical ocular and non-ocular History**

Medical history will be coded using the Medical Dictionary for Regulatory Activities (MedDRA) dictionary version 23.1. Summaries will be presented by System Organ Class (SOC) and Preferred Term (PT) with counts and percentages by treatment group and overall. Each subject will be counted only once in each SOC or SOC/PT summary.

All ocular history will be summarized by SOC and PT with counts and percentages by treatment group and overall. The summaries will be produced separately for the study eye and the fellow eye. Any ocular condition associated with both eyes will be included in both summaries.

Data listings of medical history and ocular history will be provided for the ITT set.

### **5.4. Prior and Concomitant Medications**

Prior and concomitant medications will be coded using World Health Organization (WHO) Drug Dictionary version WHO Drug Global B3-format March 2021. Non-ocular medications will be presented for the ITT set by anatomical therapeutic class (ATC) level 2 (therapeutic main group) and preferred term with counts and percentages by treatment group and overall. A subject who took more than one medication will be counted only once if these medications belong to the same extended ATC classification. In addition, prior and concomitant ocular medications used in study eye will be summarized. Similar summaries will be provided for the ocular medications used in the fellow eye. Any ophthalmological medications (ATC2 = ‘Ophthalmologicals’) that are not assigned to an eye will be presented under both eyes in the ocular medications tables and will not be presented in the non-ocular medications tables.

Prior medications will be defined as those medications taken prior to the administration of study drug on Day 1. Concomitant medications will be defined as those medications taken following the first administration of study drug on Day 1. Hence medications started before study dosing and continuing into the treatment period are considered as both prior and concomitant medications.

Separate tables will be provided for prior and concomitant medications, respectively. A data listing of prior and concomitant medications, for both ocular and non-ocular medications will be provided for the ITT set.

### **5.5. Concomitant Procedures**

Concomitant procedures will be coded using MedDRA version 23.1. Non-ocular procedures will be presented for the ITT set by preferred term with counts and percentages by treatment group and overall. A subject who had more than one procedure will be counted only once in the summary. In addition, concomitant ocular procedures in study eye will be summarized. Similar summaries will be provided for the ocular procedures used in the fellow eye.

Concomitant procedures will be defined as those procedures taken following the first administration of study drug on Day 1.

A data listing of all procedures, for both non-ocular and ocular procedures will be provided for the ITT set.

## 5.6. Exposure to Investigational Product

Exposure to the investigational product will be summarized for the ITT, mITT, and Safety sets. All analyses will be repeated for the first 12 months at both the Month 12 and final reporting as well as the full 24 months for the final reporting.

For the analysis of exposure data for the first 12 months, exposure data prior to the Month 12 visit will be summarized (i.e., the Month 12 injection will not be included in the summaries). For analyses of the full 24 months, all data will be summarized.

Injections in the fellow eye will be considered in the calculation of the duration of treatment but will otherwise be considered as a missed injection in the study eye for all other measures of exposure.

The total number of injections and total number of missed injections received in each treatment group will be summarized by treatment group to support per-injection based TEAE rates. The following categories for reason for missed injections will be summarized by treatment group using frequency counts and percentages based on the total number of missed injections: COVID-19 (with a breakdown of COVID-19 reasons as collected in the electronic case report form (eCRF)) vs. non-COVID-19 reasons (any reasons other than eCRF documented COVID-19 reasons). The total number of injections per subject will be summarized by treatment group both as a continuous summary and as a frequency and percent summary. In addition, the following categories of the total number of injections per subject will be summarized by treatment group using frequency counts and percentages:

- First 12 months summaries
  - Monthly: 1-3, 4-6, 7-9, 10-12
  - EOM: 1-2, 3-5, 5-6
- Full 24 months summaries
  - Monthly: 1-3, 4-6, 7-9, 10-12, 13-15, 16-18, 19-21, 22-24
  - EOM: 1-2, 3-5, 5-6, 7-8, 9-10, 11-12

The number of subjects who received at least 75% of the planned injections for the study period (first 12 months or full 24 months) will be presented. For the first 12 months, subjects will be considered to have received 75% of the planned injections if they received at least 9 (out of 12) injections for the Monthly group or 5 at least (out of 6) injections for the EOM group. For the full 24 months, subjects will be considered to have received 75% of the planned injections if they received at least 18 (out of 24) injections for the Monthly group or at least 9 (out of 12) injections for the EOM group.

The number of subjects missing at least one injection will be summarized by treatment group. The number of missed injections per subject as well as well as a breakdown of the number of missed injections per subject due to COVID-19 reasons and due to non-COVID-19 reasons will be summarized by frequency and counts. Additionally, for the missed injections due to COVID-19, the subjects will be summarized by their maximum drug holiday in the following categories:

- No Consecutive Injections (Subjects who are missing an injection due to COVID-19 but not at 2 injection visits in a row)
- 2 Consecutive Injections
- 3 Consecutive Injections
- 4 or More Consecutive Injections

The number of missed injections is defined as the scheduled injections missed up to completion or discontinuation of study treatment.

Additionally, the duration of treatment and compliance will be summarized by treatment group.

Duration of treatment will be defined as

- Monthly group: (date of last injection +30) – date of first injection +1
- EOM group: (date of last injection +60) – date of first injection +1

The duration of treatment will be truncated to a subject's early termination date, month 12 cutoff date, or study completion date as appropriate.

Compliance (%) is defined as the number of injections administered divided by the number of scheduled injections up to completion or discontinuation of study treatment  $\times 100$ . Compliance will be summarized in the following groups: <75%,  $\geq 75\%$  to <100%, 100%, and >100%.

The number of subjects with scheduled IVT injection visits as well as the number of subjects receiving injections at each of the Months (1-24) will also be summarized by treatment group using frequency counts and percentages. For the EOM group, any injections given on the odd-numbered months will be presented as an unscheduled injection. In addition, to assess the impact of the COVID-19 pandemic on study drug exposure, the following summary will be provided by study visit:

- Number of missed IVT injection visits for study drug
- Number of missed IVT injection visits for study drug due to COVID-19 pandemic reasons
- Number of missed IVT injection visits for study drug due to non-COVID-19 pandemic reasons

Study drug administration will be listed by treatment group. In addition, a listing of total number of injections, duration of treatment, date and day of first and last dose and number of missed injections will be provided for the ITT set.

## 5.7. Protocol Deviations

Major and minor PDVs will be assessed by sponsor personnel following Protocol Deviation Management Plan.

A PDV is classified as major if there is the potential to significantly impact the completeness, accuracy, and/or reliability of the study data, or affect a subject's rights, safety, or well-being. All PDVs will be identified and finalized prior to the analysis of the first 12 months as well as the analysis of the full 24 month and documented.

In addition, a major PDV will be derived for any subjects who did not have a valid GA lesion area assessment for either Month 10 or 12 and who had not discontinued treatment prior to Month 12. The category for this deviation will be “Study Conduct/Procedures”, the subcategory will be “Study Assessment”, and the study specific category will be “No valid GA lesion area assessment for either Month 10 or Month 12”.

PDVs will be presented for the ITT set by deviation category, subcategory, and study specific category with counts and percentages by treatment group and overall. In addition, similar summaries will be provided for major PDVs as well as for PDVs due to the COVID-19 pandemic.

All PDVs will be listed for the ITT set.

## 6. EFFICACY ANALYSES

Efficacy analysis including primary, key secondary, secondary, and exploratory analysis will be performed primarily using the mITT set, with subjects grouped according to the treatment assigned at randomization. Available data from all randomized subjects regardless of adherence to the protocol will be included in the efficacy analyses; this includes data from subjects who discontinued study drug early but continued with study assessments. All efficacy data will be listed for the ITT set.

Unless otherwise noted, hypothesis testing and estimation of treatment effects will be performed with a mixed effect model for repeated measure (MMRM) that includes data from all three treatment arms (PM, PEOM, and Sham). The Sham arm will represent the pool of the two sham treatment groups: SM and SEOM (i.e., the two sham arms will be pooled into a single “control” group). All hypothesis tests for efficacy endpoints will be two-sided.

Unless otherwise noted, analysis of efficacy endpoints (primary, key secondary, secondary, and exploratory) in the overall population will be adjusted for the following randomization stratification factors (actual status) and baseline covariates:

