### For primary efficacy endpoint

- Presence of CNV in the fellow eye (yes; no)
- Baseline GA lesion area ( $< 7.5 \text{ mm}^2$  or  $\geq 7.5 \text{ mm}^2$ )

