### 6.2.2. Main Analysis of Primary Efficacy Endpoint

The primary endpoint will be analyzed in the mITT population with subjects grouped according to the treatment assigned at randomization.

A MMRM model will be used to analyze the primary endpoint. The analysis model will include treatment (PM, PEOM, sham), presence of choroidal neovascularization in the fellow eye at baseline (Yes, No) and baseline GA lesion area ( $< 7.5 \text{ mm}^2$  or  $\geq 7.5 \text{ mm}^2$ ) as fixed effects, time (study month, categorical) as a factor, the time  $\times$  treatment interaction term, and the baseline GA lesion area ( $< 7.5 \text{ mm}^2$  or  $\geq 7.5 \text{ mm}^2$ )  $\times$  time interaction term. The least square [LS] mean change from baseline to Month 12 will be estimated from the model for each of three arms as well as the comparisons of each of the three arms to each other. For other time points of interest, LS mean change from baseline will be estimated and compared between treatments. For each estimated LS mean, the corresponding 95% CI will be presented based on the model. For the comparison of the LS means, the corresponding 95% CI and the 2-sided P-value along with the percentage difference (difference in LS means between the arms/the comparison group LS mean) will be

presented. A common unstructured covariance matrix will be used to model the within-subject errors, the sandwich estimator (Diggle, Liang, and Zeger 1994) will be used to estimate the standard errors of the fixed effects parameters, and the degrees of freedom will be partitioned into between-subject and within-subject portions. If there are convergence problems with the model, then a heterogeneous autoregressive (1) covariance matrix will be used. If convergence problems still exist, an autoregressive (1) covariance matrix will be used. The LS mean of the change from baseline in the total area of GA lesion(s)  $\pm$  the standard error will be plotted over time by treatment group.

The observed values for the total area of GA lesion(s) will be summarized by treatment group and visit for both the study and the fellow eye. Summaries will present the descriptive statistics for baseline, absolute values and change from baseline data by visit.

The mean change from baseline in the total area of GA lesion (s) in the study eye  $\pm$  the standard error will be plotted over time by treatment group.

All GA lesion (s) size data will be listed for the ITT set.

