### **6.2.5. Subgroup Analyses of Primary Efficacy Endpoint**

Subgroup analyses will be performed to evaluate the consistency of the primary analysis results across subgroups defined by demographic and baseline characteristics. Analyses will be performed for the primary efficacy endpoint (change from baseline in total area of GA lesion(s) in the study eye at Month 12) for each of the following subgroups (as appropriate per actual subgroup sample size, levels with low sample size may be pooled to allow for an analysis to be conducted):

- Age Group (<75 years, 75 to <85 years, ≥85 years)
- Sex (male, female)
- Race (White, Black or African American, Asian, American Indian or Alaskan Native, Native Hawaiian or other Pacific Islander, multiple, unknown)
  - Note: If most subjects (e.g., >90%) are of a single race, this analysis will not be conducted.
- Geographic Region (United States vs Rest of World)
- Subgroups indicative of disease severity at baseline
  - Study eye baseline GA lesion size (<7.5 mm^2; ≥7.5 mm^2)
  - Study eye baseline GA lesion size categories (approximately tertiles based on APL2-303/304 combined data\*)
  - Study eye baseline NL-BCVA categories (≥70, ≥60 - <70, ≥35 - <60, <35 ETDRS letters)
  - Study eye baseline NL-BCVA categories (<60 vs. ≥60 ETDRS letters)
  - Study eye baseline LL-BCVA categories (approximately tertiles based on APL2-303/304 combined data\*)
  - Study eye baseline monocular maximum reading speed categories (approximately tertiles based on APL2-303/304 combined data\*)
  - Baseline FRI Level (1,2,3,4)
  - Study eye mean threshold sensitivity of all points categories (approximately tertiles)
- Subgroups associated with GA progression
  - Study eye baseline GA focality (multifocal, unifocal)

- Study eye baseline GA lesion location (subfoveal involvement, without subfoveal involvement)
- Baseline GA laterality (bilateral GA (with or without CNV in fellow eye) vs. Study eye GA Only)
- Baseline CNV in fellow eye (Fellow eye CNV vs. No fellow eye CNV)
- Study eye baseline LLD categories (<20 vs.  $\geq$  20 ETDRS letters)
- Study eye baseline LLD categories (approximately tertiles based on the APL2-303/304 combined data\*)
- Study eye baseline NL-BCVA (<60 vs.  $\geq$ 60 ETDRS letters) and LLD (<20 vs.  $\geq$  20 ETDRS letters) combinations

\*Approximately tertiles will be specified consistently across the APL2-303/304 studies to the nearest clinically relevant level.

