### 1.2.1. Mixed Effect Model for Repeated Measure

```
-----  
* Read Analysis data  
-----  
* In this example, repeated measures are available at  
* avisitn = 0.5 (baseline), 2 (Month 2),  
* 6 (Month 6), and 12 (Month 12)  
-----;
```

```
data ga;  
  set adam.adga;  
  if paramcd = 'SEGAORG' and  
    avisitn in (0.5, 2, 6, 12) and  
    ANL01FL = 'Y';  
  
  * trtan (actual treatment[number])  
  * 1 = APL-2 Monthly  
  * 2 = APL-2 Every Other Month  
  * 3 = pooled Sham group;  
  if trtan in (4,5) then trtan = 3;  
  
  * trt01 are trt02 are used in multiple imputation  
  * trt01 = 1 if Sham group  
  * trt02 = 1 if APL2 Monthly group  
  * trt01 = trt02 = 0 for APL2 EOM group;  
  if trtan = 3 then trt01= 1; else trt01 = 0;  
  if trtan = 1 then trt02= 1; else trt02 = 0;  
  
  * avisitc will be used in PROC TRANSPOSE;  
  if avisitn = 0.5 then avisitc = '00'; * Baseline;  
  if avisitn = 2 then avisitc = '02'; * Month 2;  
  if avisitn = 6 then avisitc = '06'; * Month 6;  
  if avisitn = 12 then avisitc= '12'; * Month 12;  
run;
```

```
*****;  
*** MAIN ANALYSIS using MMRM ***;  
*****;
```

```
proc mixed data=ga method=reml covtest empirical;  
  where avisitn NE 0.5; * exclude rows for baseline;  
  * cnv (CNV in the fellow eye)  
  * 0 = No  
  * 1 = Yes;  
  *base cat (baseline lesion size (<7.5 vs. ≥ 7.5));  
  class trtan cnv avisitn usubjid base_cat;  
  model chg = trtan cnv base_cat avisitn trtan*avisitn base_cat*avisitn  
  /cl;
```

```
repeated avisitn / subject=usubjid type=un r;  
lsmeans trtan*avisitn/pdiff cl e alpha=.05;  
ods output diffs= diff1 LSMeans= LSMean1;  
run;
```

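### The primary model leaves out lesion focality, subfoveal involvement and GA laterality, which the SAP itself ties to progression; this may cost some precision, mainly for PEOM versus sham

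*SAP*

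**What the plan says.** SAP section 6 sets the general rule that "analysis of efficacy endpoints (primary, key secondary, secondary, and exploratory) in the overall population will be adjusted for the following randomization stratification factors". For the primary endpoint the list that follows has two entries: fellow-eye CNV and baseline lesion area below or above 7.5 mm².

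SAP 6.2.2 repeats this. Beyond treatment, time and their interaction, the MMRM contains "presence of choroidal neovascularization in the fellow eye at baseline (Yes, No) and baseline GA lesion area", the latter in two categories, plus area category by time. The sample code in Appendix 1, section 1.2.1, agrees: "model chg = trtan cnv base_cat avisitn trtan*avisitn base_cat*avisitn".

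SAP 6.2.5 has a subgroup block headed "Subgroups associated with GA progression". It lists focality, subfoveal involvement, GA laterality, fellow-eye CNV, low luminance deficit (LLD, in two codings) and an NL-BCVA by LLD combination. Of these, only fellow-eye CNV is in the primary model.

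SAP 5.2 lists focality, location and laterality among the baseline characteristics. Sections 6.2.3 and 6.2.4 contain no analysis that adjusts for them.

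**The concern.** In a linear model with randomised arms, a baseline factor that predicts the outcome and is left out stays in the residual variance. The treatment estimate is still unbiased, but its standard error is larger than it needs to be. The SAP labels these factors as related to progression and has them in hand before dosing, so adjustment would need no new data.

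The SAP already adjusts for non-stratification covariates elsewhere: chart type for reading speed (6.3.2.2) and critical print size (6.4.3), and better- or worse-seeing eye for FRI (6.3.2.3) and VFQ-25 distance activity (6.4.4). Section 15 gives no reason for treating the primary endpoint differently.

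Precision matters most for PEOM versus sham, the weaker of the two comparisons in every row of SAP Table 1. Under 6.3.1, both primary tests in this study must succeed before any key secondary hypothesis can be tested, whether by the pooled route or within this study alone. A missed PEOM result therefore costs more than the PEOM claim.

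**Working it through.** **Inputs from the documents.** Means of 1.47 (PM), 1.70 (PEOM) and 2.13 (pooled sham) mm²/year; SD 1.50, with 1.40 and 1.25 also tabulated; 200 per group (SAP 3.4 and Table 1; Protocol 12.5). Two-sided alpha is 0.0495 in the power table and 0.0496 in SAP 6.2.1. The differences from sham are 2.13 − 1.70 = 0.43 and 2.13 − 1.47 = 0.66.

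**Step 1: reproduce the stated power.** For a one-way ANOVA contrast, use a noncentral t with 3 × 200 − 3 = 597 df and noncentrality difference / (SD × √(2/200)).

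- PEOM: 0.43 / (1.50 × 0.1) = 2.867. Power at alpha 0.0495 is 81.53% (stated 81.5%).
- PM: 0.66 / 0.15 = 4.40. Power is 99.24% (stated 99.2%).

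The other pairwise cells of the table also reproduce. At alpha 0.0496, PEOM power is 81.56%.

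**Step 2: effect of added covariates.** Let R² be the further share of residual variance that the omitted factors explain. The documents do not give it, so every value below is an assumption. The residual SD becomes 1.50 × √(1 − R²) and the equivalent group size is 200 / (1 − R²). Alpha is 0.0496.

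| R² (assumed) | Residual SD | Fall in SE | Equivalent n per group | PEOM power | PM power |
|---|---|---|---|---|---|
| 0% | 1.500 | none | 200 | 81.6% | 99.24% |
| 2% | 1.485 | 1.0% | 204 | 82.3% | 99.33% |
| 5% | 1.462 | 2.5% | 211 | 83.5% | 99.45% |
| 10% | 1.423 | 5.1% | 222 | 85.4% | 99.62% |
| 20% | 1.342 | 10.6% | 250 | 89.2% | 99.84% |

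At the smaller tabulated SDs less is at stake. With SD 1.40, PEOM power goes from 86.5% to 88.2% (R² 5%) or 89.8% (10%). With SD 1.25 it goes from 92.9% to 94.1% or 95.1%.

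**Step 3: what an R² of that size requires.** A binary factor with prevalence p whose levels differ in 12-month growth by d explains p(1 − p)d² / SD² of the variance. With p = 0.5 and SD 1.50:

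- d = 0.5 mm² gives 0.25 × 0.25 / 2.25 = 2.8%.
- d = 1.0 mm² gives 0.25 × 1.0 / 2.25 = 11.1%.
- R² of 5% from one factor needs d = √(0.05 × 2.25 / 0.25) = 0.67 mm², about the planned PM effect of 0.66. Spread equally over three independent factors, it needs √(0.05 / 3 × 2.25 / 0.25) = 0.39 mm² each.

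All of this must be net of lesion area category and fellow-eye CNV.

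**Step 4: size of the change.** FAF is scheduled at Months 2, 4, 6, 8, 10 and 12. Three binary factors with visit interactions add 3 × 6 = 18 parameters, or 36 if each also has an ungradable level. The 24-month model has 12 FAF visits, so both counts double.

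**The case against.** The strongest reply is that nothing is wrong with the planned analysis. It adjusts for both stratification factors, and the estimate is valid without further covariates. That stands. A reader might infer bias or an inflated type I error from the omission; the documents support neither.

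A reader might also infer that the SAP ignores its own list, or that a loss of precision is established. Neither follows. Fellow-eye CNV comes from that list and is in the model. The heading introduces checks of consistency across subgroups; it gives no effect sizes and does not say that the factors predict growth beyond area and CNV. Laterality is defined with or without fellow-eye CNV, so it may overlap with a covariate already present.

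Nor should 81.5% be read as the power of the planned model. It is an unadjusted ANOVA figure at the largest tabulated SD, and both documents expect the longitudinal model to do better. That caveat stands only in part. With an unstructured covariance, categorical time and complete data, the Month 12 contrast is essentially a covariate-adjusted comparison at that visit. Repeated measures mainly recover information from missed visits; they do not remove variance that baseline factors could explain.

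A last objection concerns implementation. The sample code requests LS means with default equal weights across class levels. A rare ungradable level would then count for one third of its factor in each arm's LS mean, and so in the percentage difference defined in 6.2.2. An ungradable level with no subjects at some visit would make those LS means non-estimable. The treatment difference would not change. The objection is correct, and the fix has to deal with it.

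**Conclusion.** The omission is real and the SAP's own heading makes it hard to explain, but the consequence is limited to possible inefficiency. For PM, power stays between 99.2% and 99.8% over an assumed R² of 0 to 20%, so nothing turns on it. For PEOM at SD 1.50, the gain is under one point if the factors add 2% (81.56% to 82.32%), about two points at 5% and about four at 10%. These figures treat 1.50 as the residual SD of the current model, so they are indicative only; at SD 1.40 or 1.25 the gains are smaller. No document supplies the R² that would settle the size. The case for changing is that pre-specified adjustment for baseline data already collected costs little and helps the comparison on which the key secondary tests depend.

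**What to change.** Before unmasking, amend SAP 6.2.2 and the sample code as follows.

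- Add baseline focality, subfoveal involvement and GA laterality as fixed effects, each with a visit interaction. State whether LLD is included and, if not, why.
- Keep subjects with ungradable values, either by pooling them into an existing level or by using a separate level. Pooling is safer if the level could be empty at some visit.
- Compute LS means with observed-margin weights (the OM option of the lsmeans statement), using one common set of weights for all arms. This also reweights CNV and area category, so use it in the sensitivity model too; otherwise the arm means and percentage differences will not be comparable.
- Carry the same covariates into the multiple-imputation code (Appendix 1, section 1.2.2).
- Consider the same change in APL2-303, so that the two primary models stay aligned.
- Keep the current model as a sensitivity analysis and record the change in section 15.

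Section 6.2.5 already drops covariates made irrelevant by a subgroup, so it needs no new rule. The cost is about 18 parameters through Month 12 (36 with ungradable levels), which is small with about 600 subjects, plus programming work. No new data are needed. If the factors explain nothing, little is lost.
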